4. AMENDMENTS AND UPDATES

None

5. MILESTONES

Project Task or Milestone	Planned Timeframe for Completion
FSFV	May 2015
LSFV	December 2016
LSLV	December 2017
Database lock for interim analysis	March 2017
Final database lock	April 2018
Final results available	October 2018

6. RATIONALE AND BACKGROUND

Background

Metastatic renal cell carcinoma (mRCC) is the most common malignant tumour of the kidneys. Targeted therapies, which were recently introduced in the treatment of mRCC, have become the standard treatment in these patients [1]. With improved survival rate and a tolerable side effect profile, Tyrosine Kinase Inhibitors (TKIs) have largely replaced conventional immunotherapies worldwide. [2,3]

These developments have led to new research to identify the effects of these therapies on the quality of life and the treatment-related side effects.

In Turkey, due to reimbursement conditions defined by authority, cytokine (interferon alpha) treatment is the standard treatment in the first-line therapy [4]. Therefore, the data on quality of life from the pivotal studies with standard TKI treatment doesn't reflect QoL of the patients treated with TKIs as second or third line treatment in Turkey.

Rationale

TKI therapy is used after interferon alpha in Turkey due to current reimbursement status.

Therefore, the data on quality of life from the pivotal studies with standard TKI treatment doesn't reflect the QoL status of the patients treated with TKIs as second or third line treatment in Turkey. In this study, the clinical outcomes and the impact on quality of life of targeted treatments following TKIs will be explored. To our knowledge, since there is no similar reimbursement condition in the world placing IFN as the first line standard treatment, this will be the first study evaluating the QoL status with targeted therapies used as 3rd line treatment in this setting.

7. RESEARCH QUESTION AND OBJECTIVES

Research Question:

In this study, different from other studies in the literature, the data will be collected to observe the quality of life and efficacy after first line interferon alpha and second line TKI treatments.

Primary Objective:

- Measurement of health-related quality of life with targeted therapy used as 3rd line.
- Overall response rate at the end of follow up
- Median progression free survival according to RECIST version 1.1

Secondary Objectives:

- Overall survival rate
- Effect of quality of life on prognosis.
- Adverse events during 3rd line targeted treatment according to CTCAE.4.03
- Dose modifications due to adverse events
- Correlation between efficacy (overall response rate at month 12 and median PFS) and dose modifications due to adverse events
- Correlation between efficacy (overall response rate at month 12 and median PFS) and blood pressure

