PFS, OS and ORR evaluation during 3rd, 6th, 9th and 12th months performed according to RECIST version 1.1, additionally, every patient will be followed-up once for survival follow-up in order to assess the overall survival before the site close out visit. Survival follow-up will be performed via telephone visit or site visit if exist.

ORR: The best overall response is the best response recorded from the start of the study treatment until the end of treatment taking into account any requirement for confirmation. The patient's best overall response assignment will depend on the findings of both target and non-target disease and will also take into consideration the appearance of new lesions. Furthermore, depending on the nature of the study and the protocol requirements, it may also require confirmatory measurement.

PFS: The length of time during and after the treatment of a disease, that a patient lives with the disease but it does not get worse. In a clinical trial, measuring the progression-free survival is one way to see how well a new treatment works.

OS: 1 year Overall Survival (OS), defined as the time from the start of 3rd line treatment until death or 1 year due to any cause (measured at the end of follow-up).

Data Sources

The source of the data will be the electronic or the written patient records of the participating centers. The patient's data can be accessed through a patient file. In the centers, both systems can be used in conjunction. The data can be accessed using both systems.

Sample Size

This is a multi-center, national, non-interventional/observational study. In this study, patients with metastatic renal cell carcinoma who meet the inclusion criteria will be included from centers in 12 NUTS regions of Turkey. Since this is a non-interventional observational study, there is no specific follow-up protocol. In this study, approximately 152 patients will be evaluated.

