According to Turkish Statistical Institute data at the end of 2013 population of Turkey is approximately 80 million [5]. In the project of Turkey Association of Cancer Research Control which was named Cancer Record and Incidence shows that cancer incidence is 100-150 in 100.000 [6] and 2% of all new cancers are renal cell carcinoma [7]. There would be 1800 new RCC patients in 1 year, and according to the OS of the disease, there would be 4000 RCC patients in Turkey. 15% of these are metastatic at the time of diagnosis and 30-40% of these are metastatic after a period of a time [8]. Presuming that there are 1800 patients with metastatic renal carcinoma in Turkey, the minimum sample size with 7,6 confidence interval, 95% confidence level and 80% power was calculated as 152.

Data Analysis

Data Analysis:

Statistical analyses will be primarily of explorative and descriptive nature. Patients who received at least one dose of 3rd line therapy and have sufficient information whether they had an adverse event or not will be valid for safety analysis. Patients who received at least one dose of 3rd line therapy and have any information regarding efficacy of therapy will be valid for intent-to-treat efficacy analysis.

Demographic data, baseline characteristics, diagnosis and prior treatment of RCC, concomitant diseases, and concomitant medication will be described with summary statistics such as mean, SD, minimum, 1, 5, 25, 75, 95, 99 percent quartiles, median, maximum for continuous variables, and category counts and frequencies (percentages) for categorical variables. Concomitant diseases on the case report form correspond to MedDRA terms. Concomitant medication will be coded using WHO's drug dictionary.

Descriptive summaries of Kaplan-Meier (KM) estimates (including number of failed, number censored, 25th and 75th percentiles with respective 95% confidence level and median with 95% Confidence level) and KM curves will be presented for time-to-event efficacy variables (PFS, TTP, time to treatment failure). Mean, SD, minimum, 1, 5, 25, 75, 95, 99 percent quartiles, median, maximum will be produced for duration of treatment. Category counts and frequencies (percentages) will be calculated for tumor status at different visits and general subjective rating of efficacy of 3rd line therapy from the treating physician.

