8. RESEARCH METHODS

8.1. Study design

This is a multi-center post-marketing observational study. It has been defined according to the NUTS (Nomenclature of Territorial Units for Statistics: Nomenclature d'unités Territoriales Statistiques, French) criteria, which is a regional classification, created in order to reduce interregional disparities in socio-economic analysis of the regions, and to produce data comparable to that of the European Union (EU). Turkey has been divided into 12 NUTS regions depending on the economic, social, cultural, and geographical aspects, and the population size. In this study, patients with metastatic renal cell carcinoma from centers in 12 NUTS regions of Turkey will be included, who meet the inclusion criteria. Since this is a non-interventional observational study, there is no specific follow-up protocol. In this study, approximately 152 patients planned to be recruited in a year and followed-up 12 months.

This is a multi-center post-marketing observational study. In this study, patients with metastatic renal cell carcinoma from centers in 12 NUTS regions of Turkey will be included,

who meet the inclusion criteria. Since this is a non-interventional observational study, there is no specific follow-up protocol.

Presuming that there are 1800 patients with metastatic renal carcinoma in Turkey, the minimum sample size was calculated as 152.

There will be a total of 25 centers in various cities of Turkey.

The centers will consist of medical oncology clinics.

In this study, the patient follow-up period is 12 months. Each patient will be followed up to 5 times; the data will be collected at baseline, the 3rd, 6th, 9th and 12th months according to the routine practice. Additionally, every patient will be followed-up once for survival follow-up in order to assess the overall survival before the site close out visit. Survival follow-up will be performed via telephone visit or site visit if exist.

Because of the observational nature of the study, there is no predefined treatment protocol. The participating physician will continue to treat the patients at his/her own discretion. Frequency of visits will be continued per physician's preference.

The patients will be asked to fill in the quality of life questionnaire (FKSI-15, EQ5D-3L, FKSI-DRS) on each visit.

The assessment of the side effects will be based on the "Common Terminology Criteria for Adverse Events". The CTCAE V.4.03 will be used.

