8.7. Data analysis

Statistical analyses will be primarily of explorative and descriptive nature. All issues concerning patient validity, data consistency checks, permissible data modifications will be described in detail in the Data Management Plan.

Patients who took at least one dose of 3rd line treatment and have sufficient information whether they had an adverse event or not will be valid for safety analysis. Patients who took at least one dose of 3rd line treatment and have any information regarding efficacy of 3rd line treatment will be valid for intent-to-treat efficacy analysis.

Demographic data, baseline characteristics, diagnosis and prior treatment of RCC, concomitant diseases, and concomitant medication will be described with summary statistics such as mean, SD, minimum, 1, 5, 25, 75, 95, 99 percent quartiles, median, maximum for continuous variables, and category counts and frequencies (percentages) for

categorical variables. Concomitant diseases on the case report form correspond to MedDRA terms. Concomitant medication will be coded using WHO's drug dictionary.

Descriptive summaries of Kaplan-Meier (KM) estimates (including number of failed, number censored, 25th and 75th percentiles with respective 95% confidence level and median with 95% confidence level) and KM curves will be presented for time-to-event efficacy variables (PFS, TTP, time to treatment failure). Mean, SD, minimum, 1, 5, 25, 75, 95, 99 percent quartiles, median, maximum will be produced for duration of TKI treatment. Category counts and frequencies (percentages) will be calculated for tumor status at different visits and general subjective rating of efficacy of TKI from the treating physician.

Adverse events will be summarized using the MedDRA and the CTCAE coding system. Event rates for single adverse events will be calculated based on the total number of patients valid for safety. Adverse events will be categorized according to relation, seriousness, CTCAE grade (version 4.03), and discontinuation of therapy, action taken and outcome. Serious adverse events and unexpected or unlisted ADRs will be evaluated separately.

Category counts and frequencies (percentages) will be calculated for overall tolerability.

The factors, which might have impacted the duration of treatment, will be studied by retrospectively.

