The best overall response is the best response recorded from the start of the study treatment until the end of treatment taking into account any requirement for confirmation. On occasion a response may not be documented until after the end of therapy so protocols should be clear if post-treatment assessments are to be considered in determination of best overall response. Protocols must specify how any new therapy introduced before progression will affect best response designation. The patient's best overall response assignment will depend on the findings of both target and non-target disease and will also take into consideration the appearance of new lesions.

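### The objectives word ORR as a rate at a time point while the plan defines it as best response on treatment, and the set called intent-to-treat leaves out treated patients with no efficacy record

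*Combined protocol and SAP*

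**What the plan says.** **Objectives.** Section 7 and the Abstract list "Overall response rate at the end of follow up" as one of three items under the primary objective. A secondary objective reads "Correlation between efficacy (overall response rate at month 12 and median PFS) and dose modifications due to adverse events", and a second one relates the same efficacy measures to blood pressure. Section 8.1 states: "In this study, the patient follow-up period is 12 months".

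**Definition.** The Abstract, under Variables, gives "ORR: The best overall response is the best response recorded from the start of the study treatment until the end of treatment". The Abstract's data analysis text and section 8.7 repeat it: "The best overall response is the best response recorded from the start of the study treatment until the end of treatment".

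**Outcome measures.** The closing paragraph of section 8.1 gives ORR a window that opens at enrollment and closes at objective response. Section 8.2.1 admits patients who have already had up to one month of third-line treatment.

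**Tumor status by visit.** Section 8.7 adds: "Category counts and frequencies (percentages) will be calculated for tumor status at different visits".

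**Efficacy set.** Section 8.7 requires at least one third-line dose and that patients "have any information regarding efficacy of 3rd line treatment will be valid for intent-to-treat efficacy analysis". The Abstract has the same condition: "have any information regarding efficacy of therapy will be valid for intent-to-treat efficacy analysis".

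**Open rules.** Section 8.7 says that a protocol has to settle how new therapy before progression and post-treatment assessments affect best response, and then settles neither. The Abstract leaves open whether response must be confirmed.

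**The concern.** Response status at a fixed visit and best response over treatment are different quantities. Responders who later progress count in the second and not in the first. Month-12 tumor status will be tabulated in any case, so both numbers will exist at the analysis. If the objectives name one and the definition names the other, two analysts could report different values for a primary result from the same data.

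The efficacy set raises a second question. A set conditioned on having outcome information is not intent-to-treat in the usual sense. It can remove patients from the denominator of ORR but never from the numerator. The plan does not say whether a survival contact alone counts as efficacy information. Nor does it say how a patient in the set without a tumor assessment is counted.

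**Working it through.** **The plan's own figure.** The only number involved is the sample size of 152 (section 8.5), used here as the denominator and not disputed. With 95% confidence, a half-width of 7.6 points, a population of 1800 and an assumed proportion of 0.5:

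- n0 = 1.96² × 0.25 / 0.076² = 166.3
- n = 166.3 / (1 + 165.3/1800) = 152.3, which reproduces 152

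**Definitions side by side.** Response is scheduled at months 3, 6, 9 and 12 (section 8.3). Take a patient with a partial response at month 3 and progression at month 9.

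| Source | Wording of ORR | Responder? |
|---|---|---|
| Abstract (Variables; Data Analysis), 8.7 | Best response, start to end of treatment | Yes |
| 8.1, outcome measures | Enrollment to objective response | Yes |
| 7, correlation objectives | Rate at month 12, read as status | No |
| 7, primary objective | Rate at end of follow-up | No if read as status; yes if read as cumulative |

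The enrollment start in section 8.1 differs from treatment start by at most one month. It should move few responses, because response is first scheduled at month 3.

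**Size of the definition gap.** The documents give no expected ORR, response duration or onset, so this is an illustration only. Let p be the best-response rate, o the month of onset and d the median response duration, with exponential decay:

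- gap = p × [1 − exp(−ln 2 × (12 − o)/d)]
- Assumed ranges: o = 3, 6 or 9 months; d = 4 to 18 months

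| Assumed p | Smallest gap (o = 9, d = 18) | Largest gap (o = 3, d = 4) |
|---|---|---|
| 5% | 0.5 points | 4.0 points |
| 10% | 1.1 points | 7.9 points |
| 20% | 2.2 points | 15.8 points |

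At p = 10% with onset spread equally over months 3, 6 and 9, the gap is 2.0 to 6.1 points. The range is wide because every input is assumed.

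**Denominator.** Let R be the recorded responders, N all treated patients and m those dropped for lack of efficacy information. No dropped patient has a recorded response, so R/(N − m) ≥ R/N, with equality only if m = 0 or R = 0. For an assumed rate of 10%:

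- 2% dropped (about 3 of 152): 0.10/0.98 = 10.2%
- 5% dropped: 0.10/0.95 = 10.5%
- 15% dropped (about 23 of 152): 0.10/0.85 = 11.8%

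The rise is 0.2 to 1.8 points. The sampling margin is 1.96 × √(0.10 × 0.90/152) = 4.8 points.

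**The case against.** The strongest reply is that the plan does settle the definition. The Abstract puts the label ORR directly on best response, and section 8.7 repeats that definition. The section 8.1 window closes at objective response, which fits ever having responded and does not fit status at a set month. No passage defines ORR as month-12 status. The primary wording can mean the cumulative rate known once follow-up ends. Most of this stands. A reader might infer that the primary endpoint is undefined, and the documents do not support that. What survives is that the objectives do not use the stated definition. The month-12 wording in the correlation objectives is the clearer conflict, since it names a visit whose tumor status is tabulated separately. Even on the cumulative reading, end of treatment need not coincide with end of follow-up.

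On the efficacy set, the reply is that the condition is broad. Visit-level tumor status and the physician's efficacy rating both feed the analysis, and section 8.8 provides for queries on missing data and full source verification. Few patients may be dropped. That also stands, and it points to the low end of the range. A reader might infer serious inflation of ORR, but only much higher assumed exclusion rates would produce it, and nothing in the documents suggests them. Nor does the rule prove bias against the true response rate, which depends on who is missing. The one-way effect is relative to counting all treated patients with unassessed patients as non-responders.

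**Conclusion.** The point holds as an inconsistency to be aligned. Best response is the better-supported reading, but the primary and correlation objectives are not worded to match it, and the same data can give a different value under the time-point reading. How far apart the two values would be cannot be derived from the documents; the figures above rest entirely on assumed rates, durations and onsets.

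The efficacy set is mislabeled, and it can only leave ORR unchanged or raise it relative to all treated patients. The likely size is small: 0.2 to 1.8 points at an assumed 10% rate with 2% to 15% excluded.

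A reader might also infer a loss of type I error control or power. That does not follow, because section 8.5 states that no hypothesis is tested and section 8.7 describes the analyses as primarily exploratory and descriptive. The harm is to the reported estimate. It should be fixed; confidence is medium to high.

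**What to change.** 1. In sections 3, 7, 8.1 and 8.7, define ORR as the proportion of patients with RECIST 1.1 CR or PR as best overall response, counted from the first third-line dose. Use it for the primary objective. In both correlation objectives use each patient's responder status (yes or no) on the same definition. Align the section 8.1 window, and label month-12 tumor status as a separate descriptive result.
2. Take all enrolled patients with at least one third-line dose as the ORR denominator, and count those without a response assessment as non-responders. Keep the set with some efficacy information as a sensitivity analysis, and do not call it intent-to-treat.
3. As housekeeping in the same amendment, state the rules that section 8.7 itself calls for (new therapy before progression, post-treatment assessments) and whether confirmation is required. Which rule to adopt is the sponsor's choice.

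**Cost.** This needs a protocol or SAP amendment, with IRB/IEC approval if the protocol changes (section 9.3). It needs no new visits or scans. Other treatment during follow-up is already collected with dose and duration, so it is enough to check that the e-CRF holds start dates. The reported ORR may be slightly lower. Counting unassessed patients as non-responders is conservative if some did respond, and the sensitivity analysis shows the other side. Enrollment was planned from May 2015, before version 2.1 of March 2016, so the change should be made before the interim database lock planned for March 2017 (section 5).

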Outcome Measures are overall objective response rate (ORR) [Time frame: from enrollment to objective response], progression-free survival (PFS) [Time frame: from enrollment to disease progression or death, whichever occurs first], overall survival (OS) [Time frame: from enrollment to death or the end of the study duration] and probability of patient survival at 1 year [Time frame: from enrollment to 1 year]

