8.3. Variables

The outcome variables for the objective(s) are time to treatment failure (from start of treatment to progression or permanent discontinuation), overall survival (from start of treatment to the date of last follow up or death), therapeutic response to therapy based on response evaluation criteria in solid tumors (RECIST version 1.1), and safety (type, incidence, severity of adverse events graded by the National Cancer Institute [NCI] CTCAE V.4.03)

Variable	Role	Data source(s)	Operational definition
Age, gender, height, weight, blood pressure, socio-demographic characteristics	Baseline characteristic	Medical Records	
Concomitant diseases	Baseline Characteristic	Medical Records	
Medication	Baseline Characteristic	Medical Records	
Histopathological findings	Baseline Characteristic	Medical Records / Pathology Reports	
Surgical Operations	Baseline Characteristic	Medical Records	
The cytokine (interferon alpha) usage in the first-line treatment, TKI usage in the 2 nd line treatment and the dosage and the duration of the treatment	Baseline Characteristic	Medical Records	
Metastatic features	Baseline Characteristic	Medical Records	
MSKCC risk factors	Baseline Characteristic Follow-up Characteristic	Medical Records	
3 rd line treatment	Baseline Characteristic Follow-up Characteristic	Medical Records	

	Close-out Characteristic		
The performance score before the second and third-line treatment		Medical Records	
The quality of life questionnaire (FKSI-15, EQ5D-3L, FKSI-DRS) on each visit	Baseline Characteristic Follow-up Characteristic Close –out Characteristic	Patient interview	
Blood pressure		Patient diary	
Other treatment during follow-up, if any, the dose and the duration	Follow-up Characteristic	Medical Records	
Treatment of the side effects, interruption of the treatment, dose reduction, dose-elevation	Baseline Characteristic Follow-up Characteristic	Medical Records	
Duration of PFS, OS and ORR	Follow-up Characteristic Close-out Characteristic	Medical Records	

Schedule Procedure	Initial visit	Follow-up 3.month	Follow-up 6.month	Follow-up 9.month	Follow-up 12.month	Survival Follow-up
Demographic data	X					
Histopathological Findigs	X					
Medical history	X					
Previous therapy of mRCC	X					
MSKCC Risk Factors	X	X	X	X	X	
Surgical Operations	X					
Metastases Information	X					
FKSI-15, EQ5D-3L, FKSI-DRS Questionnaire	X	X	X	X	X	
Evaluation of PFS,OS and ORR		X	X	X	X	
Concomitant medication	X	X	X	X	X	
Visit date	X	X	X	X	X	

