8.6. Data management

The data will be analyzed using the statistical package program. The categorical variables will be given as number and percentages, and the continuous variables will be presented as averages and standard deviations. For between-group comparisons of categorical variables, the chi-square test will be used. The continuous variables will be tested for normal distribution using the Kolmogorov-Smirnov test and the Shapiro Wilks test. For the normally distributed continuous variables, the parametric tests (the t-test, the ANOVA, the repeated measures analysis of variance, etc.), and for the continuous variables without a normal distribution, the non-parametric tests (the Mann-Whitney U test, the Kruskal Wallis analysis of variance, the Friedman Analysis of Variance, etc.) will be used. The level of significance will be taken as $p = 0.05$.

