9.4. Ethical Conduct of the Study

The study will be conducted in accordance with legal and regulatory requirements, as well as with scientific purpose, value and rigor and follow generally accepted research practices described in Guidelines for Good Pharmacoepidemiology Practices (GPP) issued by the International Society for Pharmacoepidemiology (ISPE), Good Epidemiological Practice (GEP) guidelines issued by the International Epidemiological Association (IEA).

This is a non-interventional study where the 3rd line targeted treatment are prescribed in the usual manner in accordance with the terms of the marketing authorization. There is no assignment of a patient to a particular therapeutic strategy, the treatment decision falls within current practice and the prescription of the medicines is clearly separated from the decision to include the patient in the study. No additional diagnostic or monitoring process is required for participation or during the study. Epidemiological methods shall be used for the analysis of the collected data.

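### The objective relating median PFS to adverse-event dose modifications has no exposure-timing rule, and grouping patients as ever versus never modified would build in immortal-time bias

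*Combined protocol and SAP*

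**What the plan says.** Sections 3 and 7 list the secondary objective "Correlation between efficacy (overall response rate at month 12 and median PFS) and dose modifications due to adverse events".

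Section 8.3 records "Treatment of the side effects, interruption of the treatment, dose reduction, dose-elevation" as both a baseline and a follow-up characteristic, and leaves the operational definition empty. No section says which changes count, over what window, or how they are to be related to PFS.

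Three places bear on method:
- Section 8.6 gives chi-square for categorical variables and parametric tests for normally distributed continuous ones. For the others, "the non-parametric tests (the Mann-Whitney U test, the Kruskal Wallis analysis of variance, the Friedman Analysis of Variance, etc.) will be used". It sets significance at 0.05.
- Section 8.7 is descriptive for PFS: "KM curves will be presented for time-to-event efficacy variables (PFS, TTP, time to treatment failure".
- Section 9.4 adds only "Epidemiological methods shall be used for the analysis of the collected data".

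The clocks differ. Section 8.1 has "progression-free survival (PFS) [Time frame: from enrollment to disease progression or death, whichever occurs first". The Abstract's one-year OS is "defined as the time from the start of 3rd line treatment until death or 1 year due to any cause", and section 8.3 starts both OS and time to treatment failure at the start of treatment. Section 8.2.1 admits patients who have already had up to one month of third-line therapy, so these origins are not the same day.

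**The concern.** A median PFS belongs to a group, so the objective invites a split into modified and unmodified patients. Modifications accrue over the same 12 months in which patients progress or die. A patient whose PFS ends early has little time to be modified and tends to fall in the never group. A patient in the ever group must, by construction, have been event-free up to the modification. Neither a fixed-group test nor a Kaplan-Meier plot by final status corrects for this.

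At stake is a secondary statement that dose modification goes with longer PFS, supported by p below 0.05, when the grouping alone produced it.

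**Working it through.** **The plan's own figure.** The only computed figure is N = 152. It reproduces as the precision of one proportion (p = 0.5 assumed): 1.96² × 0.25 / 0.076² = 166.3, and with the finite population of 1800, 166.3 / (1 + 165.3/1800) = 152.3. It has no link to this objective.

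**Inputs.** From the documents: 152 patients, 12 months' follow-up, visits at months 3, 6, 9 and 12, PFS ending at progression or death, significance level 0.05. The documents give no PFS median and no modification rate or timing. Assumed: exponential PFS with median 3 to 6 months; modification at 0.05 to 0.20 per month, or confined to an early window in 40% of patients; no effect of modification on PFS.

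**Step 1: closed form.** Let λ = ln 2 / 4 = 0.1733 (true median 4 months), μ the modification rate, and a = λ + μ. Events are dated when they occur. For t < 12, the probability of PFS beyond t and no modification is

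N(t) = (λ/a)(e^(−at) − e^(−12a)) + e^(−12a).

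The never-modified curve is N(t)/N(0). The ever-modified curve is [e^(−λt) − N(t)] / [1 − N(0)].

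| μ per month | a | N(0) | Never: median | Ever: median |
|---|---|---|---|---|
| 0.05 | 0.2233 | 0.791 | 3.2 | 8.0 |
| 0.10 | 0.2733 | 0.648 | 2.6 | 7.5 |
| 0.20 | 0.3733 | 0.470 | 1.9 | 6.8 |

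Every patient has the same true median of 4 months; the gap comes from the grouping alone.

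**Step 2: log-rank on ever versus never, simulated cohorts of 152, no true effect.**

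| Modifications | Progression dated | Significant at 0.05 |
|---|---|---|
| Throughout follow-up | when it occurs | 97-100% |
| Throughout follow-up | at 3-monthly visits | 81-100% |
| First 6 months only | at 3-monthly visits | 25-46% |
| First 1, 2 or 3 months only | when it occurs | 8-16%, 22-41%, 37-65% |
| First 1-3 months only, no deaths | at 3-monthly visits | 4-6% |
| First 3 months only, deaths 15-30% of hazard | at 3-monthly visits | 4-17% |

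Monte Carlo error is about 1.5 points near 5% and 3-4 points near 50%.

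**Step 3: hazard ratios.** A larger simulation used 12,000 patients per scenario, medians of 3 to 9 months, 30-70% modified by month 12 in the absence of progression, deaths making up 15% of the event hazard, and progression dated at visits. Ever versus never gave 0.45-0.58 against a true 1.00. At a 6-month median with 50% modified, the hazard ratio was 0.53 and the apparent medians 11.7 versus 6.0 months.

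**Step 4: the exception.** With all modifications before month 3, progression recordable only from month 3 and no deaths, the hazard ratio was 0.98-1.02. With deaths at 15-30% of the hazard it was 0.86-0.91. With all modifications in the first month (deaths 15%) it was 0.94-0.98. So the bias disappears only when essentially all modifications precede the first PFS event, and that event may be a death. Section 8.1 also leaves visit frequency to the physician, so month 3 is not a guaranteed earliest date for recorded progression.

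**Step 5: the remedy on the same assumptions.** The time-dependent Cox model rejected in 4-7% of cohorts and the month-3 landmark in 3-9%. In the larger simulation their hazard ratios were 0.96-1.06 and 0.95-1.08.

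**The case against.** The strongest reply is that the criticised analysis is nowhere in the plan. The objective says only that a correlation will be examined. Modifications could be counted in a fixed window, the lists in section 8.6 are open-ended, and section 9.4 leaves room for a suitable method. The log-rank test is not named at all. This stands: a reader might infer that the plan prescribes a biased comparison, and it does not. What can be said is that it names no method that handles timing and excludes none that fails to.

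A second reply concerns direction. The simulations make modification independent of prognosis, so only the timing component can appear. If frail patients both progress and are modified sooner, the net result can reverse. With assumed frailty (log-normal SD 0.5-0.8, median 4 months), visit-dated progression and modifications only in the first 3 months, log-rank wrongly showed harm in 33-76% of cohorts and benefit in none. With modifications throughout, false benefit still dominated. This also stands: the documents do not support the inference that the reported estimate must favour modified patients.

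Third, the result depends on what is counted. If modifications after progression also count, the ever/never hazard ratio moves to 0.98-1.00 without deaths and 0.78-0.83 with them. That is a reason to write the rule, not to omit it.

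A reader might also extend these figures to the blood-pressure objective ("Correlation between efficacy (overall response rate at month 12 and median PFS) and blood pressure") or to month-12 response. The documents give no distribution of readings and no response rate, and the blood pressure diary is a separate document, so no size can be attached to either.

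Finally, sections 8.5 and 8.7 describe the study as exploratory with no hypothesis to test. That limits the consequence, but section 8.6 still sets a significance level.

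**Conclusion.** The concern holds in conditional form. The timing rule is missing, and the named methods applied to ever- versus never-modified patients would bias the timing component of PFS towards modified patients, unless essentially all modifications precede the first PFS event (progression or death).

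The size rests on assumed medians, modification rates and dating of progression. It runs from roughly 80-100% false benefit by log-rank with modifications throughout follow-up, to little or none when they are all early and progression is dated only at the 3-monthly visits. The net direction in real data is not established, because confounding by frailty or agent may act either way. The primary objectives and N = 152 are untouched. This should be fixed before analysis because a better method is available at little cost.

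**What to change.** Add to section 8.7:

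1. One time zero for PFS, reconciling enrolment (section 8.1) with the start-of-treatment clocks (Abstract and section 8.3). If enrolment is used, modifications already made count as present from time zero. If start of third-line treatment is used, patients enter the risk set only at enrolment.
2. Which recorded changes count as adverse-event-related modification for this analysis, counting only those before the PFS event.
3. No comparison of ever- with never-modified patients. Analyse PFS by a Cox model with modification as a time-dependent covariate (0 until the first, 1 afterwards), adjusted for baseline MSKCC risk and ECOG. As an alternative or a companion display, show a prespecified month-3 landmark among patients still event-free, treating progression found at the month-3 visit as before the landmark.
4. For the month-12 response comparison, state whether response means best overall response or response held at month 12, and count only modifications up to the landmark.
5. Report the results as associations.

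The cost is SAP text, modest programming and confirmation that the e-CRF dates each dose change; section 8.3 lists the changes but not their dates. With no loss to follow-up, PFS events number 152 × (1 − 2^(−12/median)), or 114 to about 142 at medians of 6 to 3 months, enough for the model. The landmark display loses patients with an event by month 3: 1 − 2^(−3/median), or 29-50% at those medians, leaving about 107 to 76 of 152. The time-dependent model keeps everyone.
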